Apparently, all prominent experts have consensus on enhancing cognitive functioning for better psychosocial outcomes in schizophrenia using psychosocial treatment or behavioural-training intervention of CR (Penadés et al., 2012; Eack, Greenwald, Hogarty, Cooley, DiBarry, Montrose, Keshavan, 2009). Its definition has intensely evolved to an intervention targeting cognitive

deficits using scientific principles of learning with the goal of improving functional outcomes. In fact, the outcome-oriented of recovery in CR, where the criteria consist of the following components of psychopathology, psychosocial functioning and duration its effectiveness is enhanced when provided in a context that provides support and opportunity for improving everyday functioning as concluded by the CR experts working group in 2012.

In fact, CR has shown similar efficacy in specific remediation and general remediation (CRT) in previous trial which the specific individualized remediation towards participants corresponding to their key cognitive concern of five training modules (verbal memory, visuo-spatial memory and attention, working memory, selective attention or reasoning (Franck et al., 2013) to improve particular cognitive domains. It is significantly in agreement with other findings which indicated the association with improvements across all the outcomes in cognitive performance, symptomatology and psychosocial functioning with the effect size of medium (ES=0.41), small (ES=0.28) and lower (ES=0.36) respectively (McGurk, Twamley, Sitzer, McHugo, & Mueser, 2007a).

On the other hand, the outcomes were similar across all cognitive domains although other review has revealed great improvement in the reasoning/problem solving, verbal learning and memory, and verbal working memory domains. The effect sizes for attention/vigilance and speed of processing in contrast indicated small improvement in McGurk et al.'s review (Wykes, Vyv, Cellard, Mcgurk, & Czobor, 2011), which examining the effects of CR with the effect size of d= .45 in global cognition.

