(Dickinson, Ramsey, & Gold, 2007), (Rodríguez-Sánchez, Crespo-Facorro, González-Blanch, Perez-Iglesias, & Vázquez-Barquero, 2007) and (Andersen et al., 2012). Convincingly, clinical implications has steered the focus on cognitive impairment in schizophrenia to be shifted from separable cognitive domains, and towards the construct of processing speed as a generalized measure of level of illness severity (Dickinson & Harvey, 2009; González-Blanch et al., 2011). Working memory, processing speed, and fluid intelligence are essentially connected to various aspects in daily functioning (Cassetta & Goghari, 2016). Amazingly, the processing speed and attention or working memory mediated the effects of cognitive functions on community activities and work skills, which reflects the social competence. The attention/working memory domain is associated to work skills; executive functions had a direct effect on interpersonal behaviours, while processing speed affects all three real-world behaviours. Therefore, the role played by verbal memory, working memory, and executive functioning in specific disability domains such as self-care management, family contact, vocational outcome, and social functioning were followed by interaction between processing speed and other cognitive domains (verbal memory, verbal fluency, working memory, and executive functioning) as predictors of specific functional abilities observed in schizophrenia (Sánchez et al., 2009).

Numerous reliable reviews discussed on the advantages of CR in schizophrenia patients with remarkable and promising results. The significant effect sizes were discovered in overall and separate cognitive domains based on the 26 studies (1,151 subjects) findings, including the effect sizes of d= .41 in global cognition, d= .41 in attention, d= .48 in processing speed, d= .52 in verbal working memory, and d= .47 in reasoning/problem solving (McGurk et al., 2007a).

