Earlier efforts to localize the symptoms of schizophrenia in a single brain region have been replaced by models that postulate a disruption in parallel distributed or dynamic circuits. Based on empirical data derived from both magnetic resonance and positron emission tomography, we have developed a model that implicates connectivity among nodes located in prefrontal regions, the thalamic nuclei, and the cerebellum. A disruption in this circuitry produces "cognitive dysmetria," difficulty in prioritizing, processing, coordinating, and responding to information. This "poor mental coordination" is a fundamental cognitive deficit in schizophrenia and can account for its broad diversity of symptoms (Andreasen 1998).

Cognitive dysmetria occurs because of disruptions in neural circuitry. A schizencephaly presumed to result from multiple hits occurring during the process of brain development. The concept of cognitive dysmetria suggests that patients suffering from schizophrenia have a misconnection syndrome that leads them to make abnormal association between mental representations and to lack the ability to distinguish between the self and not self or the important and the trivial. Perceptions or other information will be misconnected with inappropriate associations, leading to delusional misinterpretation (Andreasen 1999).

It is consistent with the study conducted by Rodriguez-Sanchez (2007) which wasdriven by the

hypothesis that deficits in cognition in schizophrenia may be determined by a slower speed of processing of cognitive performance. They compared the cognitive performance of people with schizophrenia and controls before and after controlling for the effect of speed of information processing on cognitive functioning. Interestingly, the results showed that when the influence of speed of processing was removed the cognitive deficits observed in people with first-episode schizophrenia disappeared. Moreover, the significant differences between patients and healthy volunteers in the performance of the Digit Symbol Substitution Test reveal that speed of processing is severely impaired in the early phases of psychosis.

Conceptual Framework of Cognitive Remediation through NEAR model of recovery in First Episode Psychosis

RESEARCH METHOD

Study design

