The simplest formula for the sample size calculation were identified through continuous outcome and equal sample sizes in both groups yields (Noordzij et al., 2010), which primary outcome of this study, a priori between-group difference at 5 months with cognitive performance, BACS composite score. A difference in cognitive function of 30.6 between the treated and control group $(\mu 1-\mu 2)$ with the SD of 49.9 (Rodríguez-Sánchez, Crespo-Facorro, González-Blanch, Perez-Iglesias, & Vázquez-Barquero, 2007) is considered as clinically relevant and specified such an effect to be detected with power of 80% power (0.80) and a two-sided alpha of 0.05 and beta of 0.20. This requires 42 participants to be randomised to each arm. Assuming 20% of attrition rate, the adjusted sample size will be involved in this intervention programme is 52 participants each arm with 104 participants in total for achieving desired statistical significance for a given hypothesis.

Inclusion Criteria

The inclusion criteria is established to recruit clinically stable participants according to DSM-V criteria for schizophrenia, schizophreniform disorder or schizoaffective disorder as diagnosis and presenting with cognitive deficits of young adults between 18 to 40 years. They will be provided a written informed consent and fulfil the criteria of cognitive measures, symptomatology and other functioning which to be considered as participants in this study. Moreover, they should be able to understand and/or speak a Malay language, read and write in Malay and/or English as well as able to give informed consent as considerations for being a participant in this study.

Exclusion Criteria

Participant can be excluded if they have previous diagnosis of mental retardation, psychotic disorder related to a general medical conditions or substance-induced psychotic disorder as well as concurrently undergo other types of CRT. The participation in the study is voluntary and

participants are free to withdraw from the study at any time for any reason without consequences for treatment possibilities. The researcher may decide to terminate the study at any time. Participants will be informed if the study is terminated and follow-up visits will be arranged if needed. They may also be withdrawn from the study at any time at the discretion of the researcher.

Measures and Instruments

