The descriptive statistics will be used to report the participants in terms of demographic and clinical data as well as inferential analysis such as t-test analysis for mean score of the post test. Hence, the Independent Sample t-tests will be used to compare participants and controls on age, years of education and premorbid IQ. The chi-square (χ 2) test will be used to compare the difference between groups in demographic characteristics. The relationship among the BACS measures will be evaluated through Pearson correlations among the composite scores by averaging all z-scores of the six primary measures. Pearson correlation for reliability and repeated measures for the validity of the test. The mixed model one-way analysis of variance (ANOVA) between and within group of intervention is expected to compare the difference between the means of pre and post treatment. The group differences on cognitive performance then analysed by the multivariate analysis of variance (MANOVA). The treatment effect on symptom and functioning outcomes will be analysed using Multiple Linear Regression (MLR) analysis. Effect sizes of the improvement in cognitive domain and psychosocial functioning will

also be calculated. The data analyses will be done using the SPSS version 22. All available data who met entry criteria will be analysed, which provided all outcomes on an intention to treat analysis (ITT) approach, assuming data which missing at random, including any significant predictors (Anaya et al., 2012).

Ethical Consideration

This study will be conducted in compliance with ethical principles outlined in the Declaration of Helsinki and Malaysian Good Clinical Practice Guideline. All potential participants will be enrolled in the study of cognitive remediation for first episode psychosis as defined in inclusion criteria. As the study involves UKM Medical Centre and government hospitals such as Kuala Lumpur Hospital, Kajang Hospital and Putrajaya Hospital, hence the approval from Ethics Committee of UKM and Ministry of Health (MOH) Malaysia ethical board (NMRR) have been obtained.

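### The 80% power is unsupported for ReMind versus NEAR: the 30.6 difference and SD of 49.9 come from a patients-versus-controls study and do not fit the BACS composite scale

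*Protocol*

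**What the plan says.** The protocol's Sample size calculation names the primary comparison as an "a priori between-group difference at 5 months with cognitive performance, BACS composite score". It then takes "A difference in cognitive function of 30.6 between the treated and control group" "with the SD of 49.9", cites a 2007 first-episode psychosis study for these figures, and calls the difference clinically relevant. The error rates are "power of 80% power (0.80) and a two-sided alpha of 0.05 and beta of 0.20". The result is 42 per arm, raised to 52 per arm (104 in total) for 20% attrition.

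Four other places bear on these inputs.

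- Processing Speed and Cognitive Dysmetria Model describes the study with the same lead author and year: "They compared the cognitive performance of people with schizophrenia and controls before and after controlling for the effect of speed of information processing". Healthy volunteers are mentioned in the same paragraph.
- Statistical Analysis gives the only definition of a composite: "composite scores by averaging all z-scores of the six primary measures".
- Research Hypothesis, Study design and ReMind Cognitive Training make the comparator active. Both arms receive cognitive remediation, and ReMind adds targeted processing speed.
- The Background cites a review of 26 studies with "d= .41 in global cognition, d= .41 in attention, d= .48 in processing speed", and a second review with d = 0.45 for global cognition. It also says that "CR has shown similar efficacy in specific remediation and general remediation (CRT) in previous trial".

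**The concern.** A sample size for a treatment comparison needs a difference and an SD for that treatment contrast on that outcome. Here both are attributed to a study that, as the protocol describes it, compared ill people with controls and tested no treatment. A gap between patients and controls does not indicate how far one form of cognitive remediation will outperform another.

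The units point the same way. An average of z-scores cannot have an SD near 50 or a group difference near 30, so the figures seem to belong to another measure. The label of clinical relevance then has no basis on the BACS composite either.

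What is at stake is how a null result is read. A reader who trusts the 80% would take a non-significant result as good evidence that targeting processing speed adds nothing. If the true increment is of the size the protocol cites for cognitive remediation, or smaller, an unadjusted analysis would miss it about 40% of the time or more.

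**Working it through.** **Inputs.** From Sample size calculation: difference 30.6, SD 49.9, two-sided alpha 0.05, power 80%, equal arms, 42 per arm before attrition. From the Background: d = 0.41 and 0.45 (global cognition) and 0.48 (processing speed).

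**1. Reproduce the plan's figure.** d = 30.6 / 49.9 = 0.613. By the normal approximation, n per arm = 2 × (1.96 + 0.8416)² / 0.613² = 41.7, rounded up to 42. At 42 per arm, power is 80.2% by the normal approximation and 79.3% by the t-test. The arithmetic is right; the problem lies in the inputs.

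**2. Check the scale.** If each z-score is standardised within the sample (SD 1) and the average correlation among the six subtests is c, the SD of their average is √((1 + 5c)/6).

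- c = 0: √(1/6) = 0.41
- c = 1: √(6/6) = 1.00

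Standardising against healthy norms could raise this somewhat, but nowhere near 49.9. A difference of 30.6 is impossible on this scale.

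**3. What 42 per arm detects.** By the normal approximation, (1.96 + 0.8416) × √(2/42) = 0.61 SD. By the t-test it is 0.62 SD.

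**4. Power at the effects the protocol cites** (42 evaluable per arm, unadjusted two-sided test):

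| d | Source | t-test | Normal approx. |
|---|---|---|---|
| 0.41 | cited, global cognition | 46% | 47% |
| 0.45 | cited, global cognition | 53% | 54% |
| 0.48 | cited, processing speed | 59% | 60% |
| 0.30 | assumption, smaller increment over active control | 27% | 28% |

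**5. Effect of baseline adjustment.** With baseline-outcome correlation r, the residual SD is multiplied by √(1 − r²), so the effective standardised effect is d/√(1 − r²). The protocol gives no r over the trial's interval, so each r below is an assumption. t-test power at 42 per arm:

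| r | √(1 − r²) | detectable difference (0.619 × factor) | power, d = 0.41 | power, d = 0.48 |
|---|---|---|---|---|
| 0.5 | 0.866 | 0.54 SD | 57% | 71% |
| 0.7 | 0.714 | 0.44 SD | 74% | 86% |

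The test-retest ICC of 0.89 given under Measures and Instruments would put power above 98% for both effects. It appears beside a two-week interval, so it is best treated as an upper bound at 5 months. Even at r = 0.89, an assumed d of 0.20 has only about 51% power.

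**The case against.** The strongest reply is that power depends only on the ratio. A wrong scale does not by itself change N, and 42 per arm does give 80% power for d = 0.61. The protocol also calls the difference clinically relevant, so it can be read as a target to detect rather than a forecast. Both points stand as far as they go. They do not rescue the calculation, because a target stated in units the outcome cannot have, and cited to a different kind of comparison, has not been justified for this outcome.

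Second, the 46% to 59% depends on the analysis. Statistical Analysis mentions a t-test on post-test means, but also a between- and within-group ANOVA of pre and post means. A change-type comparison at an assumed r of 0.7 has residual factor √(2 × 0.3) = 0.775 and gives 67% at d = 0.41 and 80% at d = 0.48. This stands, and it is why the low figures must be labelled unadjusted. The sample size paragraph itself takes no credit for baseline data.

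Third, several stronger readings are tempting and not supported:

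- That the trial lacks 80% power for ReMind versus NEAR. This needs the true effect, which the protocol does not give.
- That power fails for every effect the protocol documents. Baseline adjustment at r = 0.7 gives 86% at d = 0.48. The Background also cites 0.52 for verbal working memory, and 0.59 for psychosocial functioning when remediation is combined with rehabilitation, though neither is the primary outcome.
- That the cited trial of specific versus general remediation already tested this contrast. Its five modules did not include processing speed, and ReMind is described as an addition to NEAR. It is the nearest comparison cited, no more.
- That 30.6 is certainly the gap between patients and controls. The protocol never says what it measures, so this is a probable inference.

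**Conclusion.** The concern holds in this form: the stated 80% power is unsupported for ReMind versus NEAR. The inputs conflict with the protocol's own account of the cited study and with its only definition of the composite. The ratio that drives N exceeds the cognitive remediation effects cited for global cognition and processing speed (0.61 against 0.41 to 0.48). Those cited effects are for cognitive remediation in general. With remediation in both arms, the increment could plausibly be smaller, but the protocol does not quantify it.

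The size of the problem is unadjusted power of about 46% to 59% where 80% is claimed, and a detectable difference of about 0.62 SD. This assumes 42 evaluable per arm and a two-sided t-test at 0.05. Baseline adjustment could recover part or all of the shortfall at the cited effects, depending on a correlation the protocol does not state.

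**What to change.** In Sample size calculation:

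1. Remove 30.6, 49.9 and their citation as the source of the treatment effect.
2. Restate the calculation in BACS-M composite SD units: 42 evaluable per arm give 80% power for a between-arm difference of about 0.62 SD (unadjusted t-test), with 46% to 59% power at d = 0.41 to 0.48. Keep N at 104.
3. Show power for the baseline-adjusted comparison as a range over assumed baseline-outcome correlations, not as one value: for d = 0.41/0.48, 57%/71% at r = 0.5 and 74%/86% at r = 0.7.
4. State that a non-significant result does not exclude effects below the detectable size.

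In Statistical Analysis, make the primary comparison the follow-up BACS-M composite adjusted for the baseline BACS-M already collected.

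The cost is rewording two sections and accepting a less favourable stated power. No extra participants or assessments are needed.

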Cognitive remediation represents a broad set of activities and exercises that aim to restore or improve cognitive functioning, that is, attention, working memory, planning, and executive functions by stimulating new learning and facilitating social functioning. The ultimate goal of the intervention though is a generalization of the obtained skills in the habitual community setting. To date, several models of cognitive remediation can be assessed (Yulia Zaytseva 2013). The neuropsychological educational approach to rehabilitation (NEAR) method uses a strategy-coaching approach. After the computerized session of the training, participants elaborate and discuss in a small group the strategies that they have learned while practicing cognitive tasks and how these skills may be transposed to real life activities (A. Medalia 2009).

Newer psychosocial interventions and cognitive rehabilitation treatment approaches are framed in a positive light that are grounded in a *recovery* rather than *deficit* model. This new emphasis is based on the factors associated with improved quality of life, such as the ability to enjoy social and familial interactions, advance in educational endeavours, and performing well at work. The underlying theoretical framework comes from a developmental neuroscience perspective, which supports the idea that the brain is capable of changes and development throughout the lifespan.

Most cognitive interventions are based, in principle, on the large literature supporting the concept of brain plasticity and neurogenesis. Cognitive science assumes that skills development can occur at any age and can help advance or restore the brain's capacity for improving cognitive or social performance. Learning in a properly stimulating environment can help the patient to capitalize on brain malleability and improve functioning. In this context, cognitive remediation attempts to improve and/or restore cognitive functioning using a range of approaches (Barlati et al. 2013).

Principles underlying NEAR

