It also includes prominent computerised cognitive training, which leads to significant improvement concerning verbal memory, processing speed and executive function in patients with schizophrenia. During the first visit, the participant in this study will be asked to answer a set of questionnaires and to attempt a cognitive testing. Following that, participant will be randomised to one of the two arms. The arms are; Group 1: CR Therapy with targeted Processing Speed (ReMind) through selected commercial cognitive training and Group 2: standard CR.

Psychoeducation session on cognitive functions in schizophrenia will be conducted at the beginning of the program in group with discussion towards awareness on symptomatology, coping strategies and its importance in daily application. Participant will be required to attend the ReMind programme that they have been assigned to, twice a week for eight weeks with bridging group throughout the intervention. After completing eight weeks or 15 treatment sessions, whichever comes first, a set of neuropsychological, psychopathology and psychosocial questionnaires will be administered again to find out the benefits and effects that participants received from the intervention has remained at least until then. Before and after the intervention programme, they will be asked to fill up a survey questionnaire. Finally, 3 months after the intervention, the participants will be asked to come back for another follow up session.

Treatment approach

The strategic approaches CR adopting restorative and compensatory techniques with a transfer of training to other functional that integrated with vocational support. The use of drill and practice exercises that aim to restore cognitive functions is based on evidence for neuroplasticity and supported by evidence for functional change through targeted behavioural intervention. CR approaches may not rely solely on computerized exercises but involved therapist-guided instruction with verbal discussion to link the cognitive gains to everyday life. Furthermore, patient's motivation which is an important factor for rehabilitation success and is often utilized as a determining factor in the outcome of rehabilitation (Shapi'i, Mat Zin, & Elaklouk, 2015) particularly through computerized training.

Computers can be intimidating as well as inspiring because they can also be challenging for

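### Treatment is partly delivered in bridging groups, but the sample size and the named outcome comparisons treat participants as independent; if outcomes correlate within groups, error rates rise above 5% and 80% power is overstated.

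*Protocol*

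**What the plan says.** Participants are randomised individually to ReMind (cognitive remediation targeting processing speed) or standard cognitive remediation. Under ReMind Cognitive Training, psychoeducation is given to participants as a group at the start, and they then attend "twice a week for eight weeks with bridging group throughout the intervention". The Treatment approach section ranks the bridging group alongside the computer exercises as an essential component and ties it to transfer into everyday life. The NEAR Model section describes the same format in general terms: after the computer session, "participants elaborate and discuss in a small group the strategies that they have learned while practicing cognitive tasks". The Research Hypothesis names conventional NEAR as the comparator.

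The Sample size calculation uses a two-means formula for the "a priori between-group difference at 5 months with cognitive performance, BACS composite score". It takes "A difference in cognitive function of 30.6 between the treated and control group" "with the SD of 49.9", with "power of 80% power (0.80) and a two-sided alpha of 0.05 and beta of 0.20", and concludes: "This requires 42 participants to be randomised to each arm".

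The Statistical Analysis section names four outcome analyses: a t-test on post-test means, "The mixed model one-way analysis of variance (ANOVA) between and within group of intervention", MANOVA for cognitive performance, and multiple linear regression for symptoms and functioning. No section gives a group size, an ICC, a design effect, or a model term for bridging group.

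**The concern.** People treated in the same group share its sessions and peers, and probably its leader. If that makes their outcomes more alike than those of people in different groups, each person contributes less independent information than the analysis assumes. The groups lie within arms, so the extra group-to-group variation goes straight into the difference between arms. An analysis that ignores it gives standard errors that are too small, confidence intervals that are too narrow and p-values that are too small.

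The mixed ANOVA does not deal with this. Its two factors are arm (between) and pre/post (within); it has no random effect for bridging group. Two things are at stake: the validity of the nominal 5% level in the outcome comparisons, and the 80% power on which the trial size rests.

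**Working it through.** **Inputs from the protocol (Sample size calculation).** Difference 30.6, SD 49.9, two-sided alpha 0.05, power 0.80, equal arms, 42 per arm before attrition.

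**Step 1: reproduce the stated figure.** Standardised difference = 30.6 / 49.9 = 0.613. n per arm = 2 × [49.9 × (1.960 + 0.842) / 30.6]² = 41.74, rounded up to 42. This matches the protocol and corresponds to a design effect of exactly 1, so the figure contains no allowance for group correlation.

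**Step 2: assumptions.** The protocol gives neither group size m nor ICC. I take m from 4 to 10 and ICC from 0.01 to 0.10, with groups in both arms unless stated.

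**Step 3: formulas.**
- Design effect: DE = 1 + (m − 1) × ICC.
- Effective number per arm: 42 / DE.
- True two-sided error rate of an unadjusted 5% test: 2 × [1 − Φ(1.96 / √DE)].
- Power of a test with the correct standard error: non-central t with non-centrality 0.613 × √(42 / (2 × DE)). The degrees of freedom (df) are either 2 × 42/DE − 2 (participant level, optimistic) or 2 × 42/m − 2 (group level, conservative).

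**Step 4: worked case, m = 6, ICC = 0.05.**
- DE = 1 + 5 × 0.05 = 1.25; effective number = 42 / 1.25 = 33.6 per arm.
- Error rate = 2 × [1 − Φ(1.96 / 1.118)] = 8.0%.
- Standard error understated by 1 − 1/1.118 = 10.6%.
- Non-centrality = 0.613 × √(42 / 2.5) = 2.51. With about 65 df, power is 69.7%. With 7 groups per arm and 12 df, it is about 64%.
- If only one arm is grouped, the average DE is (1 + 1.25) / 2 = 1.125 and the error rate is about 6.5%.

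**Step 5: range.**

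| m | ICC | DE | False positives, unadjusted test | Power, participant-level df | Power, group-level df |
|---|---|---|---|---|---|
| any | 0 | 1.00 | 5.0% | 79% | not needed |
| 4 | 0.01 | 1.03 | 5.3% | 78% | 75% |
| 6 | 0.05 | 1.25 | 8.0% | 70% | 64% |
| 8 | 0.10 | 1.70 | 13.3% | 56% | 48% |
| 10 | 0.10 | 1.90 | 15.5% | 51% | 41% |

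The first row shows 79% rather than 80% because the t distribution replaces the normal approximation. The group-level values for m = 4, 8 and 10 use fractional numbers of groups and are approximate.

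**Step 6: check by simulation.** A plain t-test with 42 per arm and 40,000 runs per setting gave 8.1% for m = 6, ICC 0.05 (6.4% with one arm grouped) and 15.0% for m = 10, ICC 0.10. These agree with the formula.

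The error-rate and power columns describe different tests. The 8.0% belongs to the unadjusted test, which has about 77% power in that setting because its level is inflated. The 64% to 70% belongs to a test that holds its level.

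**The case against.** Several parts of the case on the other side stand, and they limit the claim.

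- **The ICC is unknown and may be small.** Much of the training is computerised, adapts to each user and is backed by homework. At an ICC of 0.01 and groups of 4 to 6, the error rate is only about 5.3% to 5.6%. A reader might infer that the false-positive rate definitely exceeds 5%; the protocol supports only the conditional statement.
- **Groups in both arms are an inference.** The small-group wording belongs to the general NEAR description. The bridging sentence refers to the ReMind programme, which is also the name of one arm, while the other arm is labelled only as standard cognitive remediation. Because the comparator is elsewhere called conventional NEAR, groups in both arms is the natural reading, but it is not stated. One grouped arm roughly halves the inflation.
- **Shared therapists and groups run at each hospital are not stated.** The hospitals are listed as sources of participants.
- **The error is not tilted towards ReMind.** A reader might infer a bias in its favour. Ignoring group correlation does not bias the estimated difference, and the inflation falls equally on both tails.
- **Not every planned test is affected.** The baseline t-tests and chi-square tests compare characteristics that group treatment cannot change.
- **Omitting hospital is not the fault.** With individual randomisation, and hospitals contributing to both arms, leaving hospital out does not raise the error rate. A simulation with 4 sites, 84 people and a site ICC of 0.05 to 0.10 gave about 5% under simple randomisation and 4.2% to 4.6% when balanced within site.

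The remaining objection is that a separate analysis plan could add a random effect. It could, but the sample size is fixed here with a design effect of 1, the outcome tests are named here without a group term, and a later plan cannot use group identifiers that were never recorded.

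**Conclusion.** The concern holds in conditional form. The protocol makes group sessions an essential part of treatment, then sizes the trial and names its outcome comparisons as if participants were independent. Any positive correlation within bridging groups makes the unadjusted standard errors too small and the stated power too high.

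The size rests on assumed values. For groups of 4 to 10 and an ICC of 0.01 to 0.10 in both arms, the problem runs from negligible at the low end to a threefold error rate at the high end. The middle case in step 4 is large enough to matter for a primary p-value near 0.05. Nothing in the protocol shows where in that range the trial lies, which is a reason to protect the analysis rather than to claim that a particular error rate applies.

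**What to change.** 1. State in ReMind Cognitive Training whether both arms have bridging groups, the intended group size, and whether groups are closed or rolling. Record a bridging-group identifier for every participant during delivery.
2. In Statistical Analysis, replace the unadjusted outcome comparisons with a mixed model that has a random intercept for bridging group in each arm with groups, and small-sample degrees of freedom such as Satterthwaite (available in SPSS MIXED). Leave the baseline comparisons as they are.
3. In Sample size calculation, keep the number of participants but restate power as a range over assumed group size and ICC, with degrees of freedom that match the model. For example: with 42 evaluable per arm, groups of 6 and an ICC of 0.05, power is about 64% to 70%. Quoting 70% alone would be too favourable for a model with about 12 degrees of freedom.

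A fixed effect for hospital may be added for precision, but it is not part of this correction.

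The cost is one recorded variable, some model wording, slightly wider intervals and a less favourable stated power.
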